11.4 BENEFITS AND RISKS ASSESSMENT, GROUP RELATEDNESS	35
11.5 COMPENSATION FOR INJURY	35
11.6 INCENTIVES (IF APPLICABLE)	36
12. ADMINISTRATIVE ASPECTS, MONITORING AND PUBLICATION.....	37
12.1 HANDLING AND STORAGE OF DATA AND DOCUMENTS.....	37
12.2 MONITORING AND QUALITY ASSURANCE.....	37
12.3 AMENDMENTS.....	37
12.4 ANNUAL PROGRESS REPORT	37
12.5 END OF STUDY REPORT	38
12.6 PUBLIC DISCLOSURE AND PUBLICATION POLICY.....	38
13. STRUCTURED RISK ANALYSIS.....	39
13.1 POTENTIAL ISSUES OF CONCERN	39
13.2 SYNTHESIS	39
14. REFERENCES.....	40

LIST OF ABBREVIATIONS AND RELEVANT DEFINITIONS

ABR	General Assessment and Registration form (ABR form), the application form that is required for submission to the accredited Ethics Committee; in Dutch: Algemeen Beoordelings- en Registratieformulier (ABR-formulier)
ADE	Adverse Device Effect
AE	Adverse Event
AF	Atrial Fibrillation
CB	Cryoballoon
CCMO	Central Committee on Research Involving Human Subjects; in Dutch: Centrale Commissie Mensgebonden Onderzoek
DD	Device Deficiency
DMS	Diaphragmatic Movement Sensor
eCRF	Electronic Case Report Form
GDPR	General Data Protection Regulation; in Dutch: Algemene Verordening Gegevensbescherming (AVG)
IB	Investigator's Brochure
IC	Informed Consent
ICE	Intracardiac Echocardiography
IFU	Instructions For Use
METC	Medical research ethics committee (MREC); in Dutch: medisch-ethische toetsingscommissie (METC)
LA	Left Atrium
LAPW	Left Atrial Posterior Wall
PV	Pulmonary Vein
PVI	Pulmonary Vein Isolation
SADE	Serious Adverse Device Effect
SAE	Serious Adverse Event
Sponsor	The sponsor is the party that commissions the organization or performance of the research, for example a pharmaceutical company, academic hospital, scientific organization, or investigator. A party that provides funding for a study but does not commission it is not regarded as the sponsor but referred to as a subsidizing party.
TTE	Transthoracic Echocardiogram

TTI	Time-to-Isolation
UAVG	Dutch Act on Implementation of the General Data Protection Regulation; in Dutch: Uitvoeringswet AVG
UHDx	Ultrahigh-Density
USADE	Unanticipated Serious Adverse Device Effect
WMO	Medical Research Involving Human Subjects Act; in Dutch: Wet Medisch-wetenschappelijk Onderzoek met Mensen

SUMMARY

Effect of a bigger cryoballoon on the total antral lesion size: evaluation of POLARx FIT - BETTER-FIT

Rationale: The next generation POLARx™ cryoablation balloon (CB) catheter will have the option of to deliver cryotherapy with the current balloon size of 28 mm or a new, larger 31 mm size by changing the inner balloon pressure (POLARx™ FIT, Boston Scientific). Currently, there is no data on the extension of left atrial (LA) lesion formation with the 31 mm balloon size of the POLARx™ FIT cryoablation balloon catheter. The hypothesis is that a larger CB size results in a wide antral circumferential lesion.

Objective: The primary objective is to evaluate the antral lesion size using ultrahigh-density (UHDx) mapping pre- and post-cryoablation with the 31 mm balloon size CB. Secondary objectives are the proportion of pulmonary veins (PVs) where a 31 mm CB could be positioned to achieve a grade 4 occlusion and the single shot success rate with the 31 mm balloon size CB.

Study design: Single-center, single-arm, prospective study with pre- and post-PVI UHDx mapping.

Study population: Twenty adult patients with paroxysmal AF who are scheduled to undergo pulmonary vein isolation (PVI) with a CB.

Intervention: Patients will undergo pre- and post-ablation UHDx mapping (Orion™ catheter and Rhythmia™ 3D-mapping system, Boston Scientific) during the index procedure.

Main study parameters/endpoints: The primary endpoint is the extent of the antral lesion size. Secondary endpoints are the proportion of PVs with grade 4 occlusion with the 31 mm balloon size CB, the single shot success rate of the 31 mm balloon size CB, difference in proportion of achieving grade 4 occlusion in comparison to the standard (28 mm) size.

Nature and extent of the burden and risks associated with participation, benefit, and group relatedness: A UHDx mapping will be acquired before and after complete PVI. The procedures will be performed under deep sedation, which is standard practice for CB procedures in our institution. The risk of additional mapping is limited. LA mapping is a standard diagnostic method for patients undergoing PVI with radiofrequency (“standard-of-care”). In the current study, UHDx mapping will now be used in patients undergoing PVI with CB. The most important complication of additional intracardiac mapping is cardiac tamponade, but this risk is low (<0.5%).

1. INTRODUCTION AND RATIONALE

Pulmonary vein isolation (PVI) is the cornerstone of interventional treatment of symptomatic atrial fibrillation (AF). Among the different available single-shot devices, the cryoballoon has demonstrated to be as effective and safe as radiofrequency ablation for achieving PVI, while being associated with shorter procedure duration and longer fluoroscopy time.¹⁻⁶ Furthermore, cryoballoon ablation seems to be less operator-dependent than radiofrequency ablation.⁷

Mid 2020 a novel cryoballoon (CB) was introduced for the treatment of paroxysmal AF: the 28 mm POLARx™ catheter (Boston Scientific, Marlborough, MA, USA). The initial clinical results with POLARx™ have shown a similar acute procedural efficacy and safety profile as the fourth-generation 28 mm Artic Front Advance Pro™ (AFA-Pro) CB catheter (Medtronic, MN, USA).⁸⁻¹⁷ In contrast to AFA-Pro, the POLARx™ CB operates with a constant inner balloon pressure allowing it to maintain a constant size throughout inflation and ablation. The procedure time, ablation time and fluoroscopy time are similar between POLARx™ and AFA-Pro.⁸ One-year freedom from atrial arrhythmias was 77% with POLARx™ which is also comparable with AFA-Pro.¹⁸

The next generation POLARx™ CB (POLARx™ FIT) will allow each ablation to be performed with either the standard balloon size (28 mm) or an alternative larger size (31 mm). The POLARx™ FIT catheter will expand to the standard balloon size upon every inflation. After each inflation and prior to initiating ablation, the user can increase the balloon size using the console user interface. The larger size is enabled by increasing the inner balloon pressure from 2.5 psi to 7.5 psi (which is still lower than the balloon pressure during ablation with AFA-PRO). Currently, there is limited data on the extension of left atrial (LA) scar formation with the 31 mm balloon size of the POLARx™ FIT CB. Previous quantitative data have shown that the second-generation 28 mm AFA CB creates antral lesions.¹⁹ Preliminary data demonstrated that a 31 mm balloon size will result in an antral shift in balloon position.²⁰ A wide antral lesion may potentially be beneficial for targeting ganglionic plexi and rotational activity near pulmonary vein (PV) ostia thereby potentially increasing long-term arrhythmia survival.²¹ However, there is a lack of clinical data on the use of the larger balloon size, and the benefits and limitations of the larger balloon size on occluding different pulmonary veins. The primary aim of the present study is to evaluate the antral lesion size when performing a cryoablation with the 31 mm balloon size of the POLARx™ FIT CB catheter. The secondary aim is to evaluate the feasibility of achieving a grade 4 occlusion with this larger balloon size and the single shot success.

2. OBJECTIVES

The primary objective is to determine the antral lesion area after PVI with a 31 mm balloon size POLARx™ FIT cryoballoon.

The secondary objectives are to determine the proportion of achieving a grade 4 occlusion, the single shot success rate per PV with the 31 mm balloon size POLARx™ FIT CB and the difference in occlusion quality in comparison to the 28 mm balloon size.

[figure not shown]
3. STUDY DESIGN

3.1 Study design

Investigator-initiated, single-center, open label, prospective, single-arm study evaluating the 31 mm balloon size of the POLARx™ FIT cryoballoon. Before and after complete PVI, a 3-dimensional ultrahigh-density (UHDx) map will be created. The study population will consist of 20 patients undergoing a first PVI with a normal PV anatomy (exclusion of large common ostium or supernumerary veins as determined by a preprocedural CT-scan) in the Erasmus MC, Rotterdam, the Netherlands. Patients will be seen at the outpatient clinic 3 (blanking), 6 and 12 months after the index ablation to assess potential adverse events and recurrence of atrial arrhythmias. After the 1-year visit the study will end for the individual patient. The study flowchart is depicted in Figure 3.1.1.

3.2 Estimated enrolment and study duration

Enrolment in the study is expected to take approximately 8 months. The last patient included will be followed for at least 12 months after the index procedure, thus, the total duration of the study is expected to be approximately 20 months.

Figure 3.1.1. Study flowchart

4. STUDY POPULATION

4.1 Population (base)

AF is the most common arrhythmia in the general population and is associated with an increased risk of stroke, heart failure and mortality. When patients have symptoms secondary to AF either a rate or rhythm control strategy is possible. Components of a rhythm control strategy consists of the use of antiarrhythmic medication, cardioversion, and catheter ablation. When patients have symptomatic AF despite the use of antiarrhythmic medication, they are candidates for a catheter ablation. PVI is the cornerstone of catheter ablation of AF. In the Erasmus MC, more than 300 patients with AF undergo PVI annually of whom approximately 100 patients with a cryoballoon. Most patients undergoing PVI with a cryoballoon has paroxysmal AF. This population is the target population of the **BETTER-FIT** study. A maximum of 20 patients will be enrolled in the study.

4.2 Inclusion criteria

To be eligible to participate in this study, a subject must meet all the following criteria:

1. History of symptomatic paroxysmal AF
2. Subjects who are indicated for a PVI according to the 2020 ESC guidelines for the diagnosis and management of AF²²
3. Subjects who are willing and capable of providing informed consent
4. Subjects who are willing and capable of participating in all testing associated with this clinical investigation
5. Subjects whose age is 18 years or above

4.3 Exclusion criteria

A potential subject who meets any of the following criteria will be excluded from participation in this study:

1. Any known contraindication to an AF ablation or anticoagulation
2. History of previous left atrial ablation or surgical treatment of AF, atrial flutter, or atrial tachycardia
3. AF secondary to electrolyte imbalance, thyroid disease, or any other reversible or non-cardiac cause
4. Significant structural heart disease as evidenced by:
 - a. Left ventricular ejection fraction <45% based on most recent transthoracic echocardiogram (TTE) performed <6 months prior to enrollment
 - b. LA diameter >55 mm based on most recent TTE performed <6 months prior to enrollment
 - c. Previous cardiac surgery

- d. Previous cardiac valvular surgical or percutaneous procedure
- e. Interatrial baffle, closure device, patch, or occluder
- f. Unstable angina or ongoing myocardial ischemia
- g. Moderate or severe valvular heart disease on most recent TTE performed <6 months prior to enrolment
- h. Congenital heart disease
- i. Left atrial thrombus
- 5. History of blood clotting or bleeding disease
- 6. Stroke or transient ischemic attack <3 months prior to enrollment
- 7. Active systemic infection
- 8. Common ostium PV >24 mm defined by CT-scan
- 9. Pregnant, lactating, or women of childbearing potential who are, or plan to become, pregnant during the time of the study
- 10. Subjects who are currently enrolled in another investigational study or registry that would directly interfere with the current study

4.4 Sample size calculation

With 20 patients we can provide a reliable estimate of the antral lesion area with the 31 mm balloon size of POLARx™ FIT. A recent study by Gunawardene et al. evaluated the antral lesion area in 20 patients who underwent pulmonary vein isolation with a different technique (i.e., pulsed field ablation).²³ The total circumferential antral lesion areas of the left and right sides were 20.5 ± 3.8 and $25.5 \pm 5.7 \text{ cm}^2$, respectively. The precision achieved with 20 patients thus seems adequate to provide a reliable estimate of the antral lesion area. Furthermore, the percentage of technical successful placement of the larger balloon size and the single freeze success percentage are based on the number of PVs (approximately 80 PVs in 20 patients). It is expected that 20 patients will be enrolled in a period of 8 months (approximately 30% enrolment rate of target population), thus an estimated mean inclusion rate of 2.5 patients per month.

5. TREATMENT OF SUBJECTS

5.1 Investigational product/treatment

5.1.1 Periprocedural management

All patients will receive oral anticoagulation for at least 4 weeks before ablation. Direct acting oral anticoagulants are continued in the morning of the procedure. Vitamin K antagonists will be continued with a target INR between 2.0 and 2.5. To exclude left atrial

thrombi, all patients will undergo a transesophageal echocardiogram just before the procedure.

5.1.2 Transseptal puncture

Femoral vein punctures will be performed under ultrasound guidance. After placement of 2 short introducer sheaths (8F and 10F) in the femoral vein, a bolus of intravenous heparin (5000 IE) will be given. A transseptal puncture will be performed using a SL1-sheath (Swartz, Abbott, Abbott Park, IL) and RF transseptal needle (NRG, Bayliss Medical, Rouyn-Noranda, Canada) under guidance of intracardiac echocardiography (ICE) (ViewFlex Xtra, Abbott). The SL1 sheath will be replaced by the POLARSHEATH™ (Boston Scientific). The dilator and guidewire will be slowly pulled out and the sheath is flushed thoroughly before introduction of the cryoballoon catheter. After the transseptal puncture, the ICE catheter is replaced by a steerable decapolar diagnostic catheter (Inquiry™, 2-5-2 mm spacing, St. Jude Medical). The decapolar catheter is placed in the right ventricle (for vagal response) or in the vena cava superior (for phrenic nerve pacing).

5.1.3 Pre-ablation UHDx mapping

Mapping will be preferentially performed in sinus rhythm with prior cardioversion of AF if required. UHDx mapping will be performed with RHYTHMIA HDx™ mapping system and a 64-pole mini-basket mapping catheter (INTELLAMAP ORION™, Boston Scientific). LA voltage maps will be constructed with special point density in the antra of PVs.

5.1.4 Ablation procedure

After placement of the POLARMAP™ circular mapping catheter in the target PV, the cryoballoon is initially inflated to the standard 28 mm size. The most optimal PV occlusion with the 28 mm balloon size will be achieved and the grade of PV occlusion will be determined using a semi-quantitative grading (1 – rapid outflow of contrast medium from the PV to 4 – complete contrast retention with no observable leak).²⁴ Thereafter, the balloon will increase in size to 31 mm and the most optimal PV occlusion will be achieved. Again, the grade of PV occlusion will be determined using a semi-quantitative grading (grade 0 to 4).²⁴ After optimal PV occlusion with the 31 mm balloon size, a single 3-minutes cryoapplication will be delivered, irrespective of achieving PV isolation. The cryoapplication will be prematurely stopped when the inner balloon temperature is -69°C. If PV isolation is not achieved after the first attempt, subsequent cryoapplications (3 or 4 minutes depending on TTI) are delivered until achieving isolation. The balloon size during subsequent applications can be adjusted according to the preferences of the operator.

The order of PVs will be left superior PV, left inferior PV, right inferior PV, and right superior PV. During cryoablation of the left-sided PVs, a diagnostic catheter will be placed in the right ventricle to provide ventricular pacing in case of a vagal response after cryoablation. During cryoablation of the right-sided PVs, high-output right phrenic nerve stimulation will be performed using a diagnostic catheter in the right subclavian vein or superior vena cava. Diaphragmatic excursion will be checked by a combination of manual palpitation and the use of the Diaphragmatic Movement Sensor (DMS). Whenever the diaphragmatic excursions decrease, cryoablation will be immediately terminated. The following parameters will be noted per cryoapplication: time from ablation till -40 °C, TTI, balloon nadir temperature, thawing time till 0°C.

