5.1.5 Confirmation of complete PVI

Electrical isolation of a PV is demonstrated by entrance and exit block. Entrance block is defined as the absence of local potentials inside the vein as assessed by the POLARMAP™ circular mapping catheter. Exit block is defined as absence of atrial capture while pacing from inside the vein with the POLARMAP™ circular mapping catheter. If a PV shows reconnection, repeat cryoablation will be performed with the goal of achieving electrical isolation. This can be performed with the 28 mm or 31 mm balloon size per operator discretion. Complete PVI is defined as electrical isolation of all PVs. After complete PVI, post-ablation UHDx mapping will be performed.

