5.1.6 Post-ablation UHDx mapping

After achieving complete PVI, the 64-pole mini-basket mapping catheter will be introduced through the POLARSHEATH for repeat mapping. Repeat mapping will be preferentially performed in sinus rhythm with prior cardioversion of AF if required. There will be no specified waiting time before remapping. LA voltage maps will be constructed with special point density in the antra of PVs. Post-ablation LA lesion surface area will be assessed as previously described.²³ The key parameters that will be collected are described in the Methods section. If conduction gaps or PV reconnections are found during UHDx mapping, the mapping catheter will be replaced by the POLARx™ cryoablation catheter and additional ablations will be performed to achieve complete PVI. Another UHDx map will be constructed after re-isolation.

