8. METHODS

8.1 Study parameters/endpoints

8.1.1 Main study parameter/endpoint

- Extent of antral lesion size (continuous variable) directly after cryoablation with a 31 mm balloon size POLARx™ FIT cryoablation catheter. Measures of antral lesion size are described in paragraph 8.3.1. and Table 8.3.1.1.

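### The primary endpoint is named for the 31 mm balloon, but repeat freezes before the endpoint map may be at 28 mm, and no analysis separates or examines lesions that mix the two sizes

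*Combined protocol and SAP*

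**What the plan says.** Section 2 states: "The primary objective is to determine the antral lesion area after PVI with a 31 mm balloon size". Section 8.1.1 gives the primary endpoint as "Extent of antral lesion size (continuous variable) directly after cryoablation with a 31 mm balloon size".

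Section 5.1.4 fixes the first freeze in each vein: "After optimal PV occlusion with the 31 mm balloon size, a single 3-minutes cryoapplication will be delivered, irrespective of achieving PV isolation". If isolation fails, further freezes follow, and for these "The balloon size during subsequent applications can be adjusted according to the preferences of the operator". Section 5.1.5 treats a reconnected vein in the same way: "This can be performed with the 28 mm or 31 mm balloon size per operator discretion".

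The map comes after all of this. Section 5.1.5 states: "After complete PVI, post-ablation UHDx mapping will be performed". If that map shows gaps or reconnection, Section 5.1.6 provides for more ablation, and then: "Another UHDx map will be constructed after re-isolation".

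On data, Section 5.1.4 has a list introduced by "The following parameters will be noted per cryoapplication". It names time to -40 °C, TTI, nadir temperature and thawing time, and does not name balloon size. The schedule in Section 5.1.8 has a row for procedural data that is not itemised.

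Section 10.1 and Table 8.3.1.1 describe the lesion in absolute and relative terms. Neither refers to balloon size.

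**The concern.** The stated quantity is the lesion made by the 31 mm balloon. The measured quantity is the lesion present after every freeze needed for complete PVI, some of which may be at 28 mm. Repeat freezes at 31 mm fit the stated objective and are not at issue. Where a 28 mm repeat occurs, the map shows a mixed lesion, and Section 10.1 would count it as a 31 mm lesion with no attribution rule, subgroup or sensitivity analysis.

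This bears on the trial's main result. The introduction justifies the study by the limited data on lesion extent at 31 mm, and the output is one descriptive estimate under that name.

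One 28 mm freeze can also reach beyond its own vein. Section 8.3.1 measures the circumferential area around an ipsilateral pair, so one such freeze makes that side mixed. The posterior-wall area and the three lines span both sides, so it makes the whole patient mixed. For the posterior PV antral area the reach is unclear: the text and figure caption of Section 8.3.1 describe it by side, while Table 8.3.1.1 lists it by vein.

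**Working it through.** **Inputs from the protocol.** 20 patients and about 80 veins (Section 4.4), which reproduces as 20 × 4 = 80. Single-shot isolation of 62.1% where the first freeze was at 31 mm (Section 6.3). SDs of 3.8 cm² (left) and 5.7 cm² (right) from a pulsed-field study (Section 4.4).

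**Input not in the protocol.** q, the share of veins needing a repeat that receive any 28 mm freeze. The text permits 28 mm and does not require it, so q is run from 0% to 100%.

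**Step 1: repeats.** f = 1 - 0.621 = 0.379, and 80 × 0.379 = 30.3, or about 30 veins.

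**Step 2: mixed lesions.** Per vein, p = f × q. With independent veins, a side is mixed with probability 1 - (1 - p)² and a patient with probability 1 - (1 - p)⁴. If the need for a repeat clusters fully within patients but size is chosen per vein, these become f[1 - (1 - q)²] and f[1 - (1 - q)⁴]. If both cluster fully, sides and patients equal p.

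| q | Veins (p) | Sides, independent | Patients, independent | Sides, repeats clustered | Patients, repeats clustered |
|---|---|---|---|---|---|
| 0% | 0% | 0% | 0% | 0% | 0% |
| 10% | 3.8% | 7.4% | 14.3% | 7.2% | 13.0% |
| 35% | 13.3% | 24.8% | 43.4% | 21.9% | 31.1% |
| 50% | 19.0% | 34.3% | 56.8% | 28.4% | 35.5% |
| 100% | 37.9% | 61.4% | 85.1% | 37.9% | 37.9% |

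For q = 35%: p = 0.379 × 0.35 = 0.133; side 1 - 0.867² = 0.248; patient 1 - 0.867⁴ = 0.434.

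**Step 3: the single-shot rate.** In the cited substudy only 65% of ablations were at 31 mm, so 62.1% may not carry over. At q = 35% with independent veins, an assumed rate of 80% gives p = 0.20 × 0.35 = 7.0%, with 13.5% of sides and 25.2% of patients mixed. A rate of 50% gives p = 17.5%, 31.9% and 53.7%. Re-ablation for reconnection or gaps (Sections 5.1.5 and 5.1.6) is not counted and could add to these.

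**Step 4: precision of a 31 mm-only subset.** The half-width of a 95% CI is t(0.975, n - 1) × SD/√n. The plan states no target width. With all 20 patients it is ±1.78 cm² left and ±2.67 cm² right. At q = 35% with independent veins, 20 × 0.867² = 15.0 pairs per side remain, giving ±2.10 and ±3.16 cm² (about 18% wider). For patient-level measures, 20 × 0.867⁴ = 11.3 remain, and at n = 11 the interval is about 44% wider. If only repeats cluster, about 16 pairs (14% wider) and 14 patients (23% wider) remain.

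**The case against.** The other side has four arguments.

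- **Permission is not occurrence.** A reader might infer that the trial will report mixed lesions as 31 mm lesions. The documents do not support that. Sections 5.1.4 and 5.1.5 allow 28 mm repeats, and if operators stay at 31 mm no lesion is mixed. This stands, and it is why the table starts at 0%.
- **A strategy reading is available.** Section 2 speaks of the area after PVI, and the procedure is 31 mm first and then continued to isolation. On that reading mixed lesions belong in the estimate. This is reasonable, but no sentence says so, and Section 8.1.1 ties the endpoint to cryoablation at 31 mm. It supports naming the strategy, not leaving it unnamed.
- **The consequence is limited.** The primary analysis is descriptive, with no test, threshold or 28 mm lesion comparator, so mixing cannot create a false positive. Every vein is first frozen at 31 mm, and Section 6.3 reports preliminary evidence of a more antral position at that size, so a 28 mm repeat may add little. This stands and lowers the severity. Equally, a repeat given because isolation failed might ablate tissue that the first freeze missed, and the plan has no analysis that would show which holds.
- **Balloon size may be recorded anyway.** The list in Section 5.1.4 is not the full dataset: it also omits occlusion grade, which the same section requires and Section 10.2 analyses. A reader should therefore not infer that size goes unrecorded, only that no sentence says it is recorded.

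**Conclusion.** The gap is real and modest. The endpoint is named for 31 mm, 28 mm repeats are permitted before the map that supplies it, and the analysis does not distinguish the two. If any 28 mm repeat occurs, a mixed lesion is reported as the 31 mm result with nothing beside it to show the effect.

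The frequency cannot be fixed from the documents. Across the full range of q, with independent veins and the 62.1% rate, it is 0% to 61% of sides and 0% to 85% of patients; clustering lowers the upper end. These figures are illustrative and should not be read as a forecast. They assume four veins per patient and leave out re-ablation for reconnection or gaps. The direction and size of any effect in cm² are unknown.

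A reader might also take a 31 mm-only subset as the true 31 mm lesion size. That does not follow. The subset drops veins that failed and were then frozen at 28 mm, so it is selected on outcome. Both estimates need their qualification.

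This is a cheap improvement of low to moderate severity.

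**What to change.** Treatment and operator discretion stay as they are.

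1. **Section 5.1.4:** add balloon size (28 or 31 mm) to the parameters noted for every cryoapplication, or confirm that the procedural data row in Section 5.1.8 includes it.
2. **Sections 8.1.1 and 10.1:** name the all-patient primary result as the antral lesion after complete PVI with a 31 mm-first strategy. Report the number and size of applications per vein and per side.
3. **Section 10.1:** prespecify, beside that result, a sensitivity analysis limited to units treated only at 31 mm, with repeat 31 mm freezes allowed. The units are ipsilateral pairs for the circumferential area and patients for the posterior-wall area and lines. For the posterior PV antral area they are veins or sides, once the text of Section 8.3.1 (by side) and Table 8.3.1.1 (by vein) are reconciled. Give 95% CIs for both estimates. Label the first as 31 mm-first and the second as 31 mm-only and selected on outcome.
4. **Section 5.1.6, clarification only:** state that the last map, made after complete PVI is confirmed, supplies the endpoint. The text already implies this.

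The cost is one data field, or one sentence if the field exists, and a few sentences of analysis text. The downside is that the subset is selected on outcome and less precise, which is why it stands beside the all-patient result and does not replace it. Settling point 1 early matters most: if size is not captured per freeze, mixed lesions may not be identifiable later.
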